Up to 100 current cigarette smokers will be recruited from the community surrounding Roanoke, VA. Eligible participants will be 21 to 65 years old, smoke from 5 to 40 cigarettes per day, have a breath carbon monoxide (CO) level of at least 10 ppm at intake, currently use or are willing to sample nicotine pouches, and have no immediate plans to quit smoking. Females who are planning pregnancy, pregnant, lactating, not willing to use contraception during the study, and individuals who have plans to move out of the area during the course of the experiment will be excluded from participation. Use of other tobacco/nicotine products will not be exclusionary. These minimally restrictive inclusion/exclusion criteria will allow for a broad range of participants and increase the generalizability to tobacco regulation of our eventual results.

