Hypothetical Experimental Tobacco Marketplace sessions (approximately 15-30 min). Approximately 7 days following the completion of the sampling period, participants will return to the laboratory where they will bring back SPECTRUM cigarette butts and any unused products. We will ask them to complete a Hypothetical Experimental Tobacco Marketplace. During these Hypothetical Experimental Tobacco Marketplace sessions, participants will sit in front of a computer and respond to an online marketplace where they will be able to "purchase" a variety of nicotine products (e.g., investigational cigarettes, nicotine gum, snus, nicotine pouches). Importantly, the marketplace interface mimics what participants might encounter if they shopped online for these products. In order to obtain the behavioral economic measures described earlier (e.g., demand intensity, substitutability, complementarity), participants will complete a series of purchasing scenarios where the price of cigarettes (investigational cigarettes) is manipulated (approximately 6 prices) and all other nicotine products remain at a constant price. Participants will be given an allowance equal to seven days' worth of their typical expenditure on cigarettes and/or other tobacco products and will be asked to make purchases for the following seven days. Participants will be told to make these decisions as if they will actually receive the products, but participants will not actually receive the products they purchase.

The Hypothetical Experimental Tobacco Marketplace sessions will include:

- 1.Investigational cigarette A (0.4mg/g) increases in price (across separate blocks), with no other products available
- 2.Investigational cigarette B (17.4 mg/g) increases in price (across separate blocks), with no other products available
- 3. Investigational cigarette A (0.4mg/g) increases in price (across separate blocks), all other products' prices stay the same (no conventional cigarettes).
- 4.Investigational cigarette B (17.4 mg/g) increases in price (across separate blocks), all other products' prices stay the same (no conventional cigarettes).

During the last session, participants will complete several of the tasks completed during the assessment session (e.g., cigarette and nicotine pouch valuation, delay discounting tasks for hypothetical money, Timeline Followback, Fagerström Test of Cigarette Dependence).

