## **Statistical Analysis Plan**

Participants' characteristics, including demographics and smoking-related assessments collected at a baseline session, were described using mean, standard deviation, and percentages, where appropriate. The perceived risk of HVCs was compared to the perceived risk of LVCs using a paired t-test.

Purchasing cigarettes (LVCs and HVCs) is a continuous measure, ie, the number of cigarettes purchased. In practice, participants opted to purchase either LVCs or HVCs and rarely purchased both products in the same trial (11.94% of the trials). As a result, we opted to model the purchasing of cigarettes and alternative tobacco products as a binary indicator; whether or not a participant purchased that type of cigarette in a trial. The purchasing of HVCs was estimated using a mixed-effects logistic regression to model the association between session, ventilation level (30.6% or 22.0% ventilation), and price of a HVC with a random effect for each participant due to the repeated (3) measurements study design. Similarly, the purchasing of LVCs and alternative tobacco products was estimated using a mixed-effects logistic regression to model the association between session, ventilation level (3.0% or 11.6% ventilation), and price of HVCs. Note that we included a variable for ventilation level in both models to quantify if the changes in product specifications over time influenced the overall purchasing patterns.

The proportion of the total budget spent on cigarettes was estimated using a repeated measures analysis of variance (RMANOVA) to evaluate the session's role and the price of HVCs. The total number of cigarettes purchased was also modeled using an RMANOVA, including the session and price of HVCs as independent variables. For these analyses, the price of cigarettes was categorical. Post hoc comparisons were performed using Tukey's correction for multiple testing.

For all analyses, the inclusion of the interaction between session and price of an HVC was determined by the model with the lowest Bayesian Information Criteria (BIC). After model selection, the final model to predict the total quantity of cigarettes purchased included the interaction between session and price, and the final model for all other outcome measures did not include this interaction. R software Version 3.5.1 was used for all data analysis (R Core Team, 2021). All statistical tests were considered significant at the < 0.05 level.

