A post hoc power analysis was performed with 1000 simulations using the package SIMR (Green & MacLeod, 2016). This analysis set the effect size to the smallest observed value in the results

(OR: 2.8; Purchasing patterns of low-ventilation cigarettes section). Using this effect size, the sample size of 20 participants, and an alpha of 0.05, we achieved 88% power in this study.

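### The SAP analyses a cigarette-ventilation study while the protocol describes a nicotine-content study, and no SAP model contains either factor that defines the protocol's four conditions

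*SAP*

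**What the plan says.** **Protocol.** Section 5.1 lists four marketplace conditions, all completed by every participant:

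- conditions 1 and 2: the 0.4 mg/g or the 17.4 mg/g cigarette rises in price and nothing else is for sale;
- conditions 3 and 4: the same two cigarettes rise in price while other products are for sale at fixed prices.

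Within each condition "the price of cigarettes (investigational cigarettes) is manipulated (approximately 6 prices) and all other nicotine products remain at a constant price". The stated purpose is "In order to obtain the behavioral economic measures described earlier (e.g., demand intensity, substitutability, complementarity". On numbers, section 3.1 says "Up to 100 current cigarette smokers will be recruited". Section 2.1 gives the same aim, but its list prints only items 1, 2 and 4, so section 5.1 is used here.

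**SAP.** The model for HVC purchases is meant to "model the association between session, ventilation level (30.6% or 22.0% ventilation), and price of a HVC". The model for LVCs and alternative products is meant to "model the association between session, ventilation level (3.0% or 11.6% ventilation), and price of HVCs". Two repeated-measures ANOVAs (share of budget spent on cigarettes, total cigarettes bought) use session and HVC price. A paired t-test compares the perceived risk of HVCs and LVCs. The design is said to have 3 repeated measurements.

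The text is in the past tense and contains findings. Participants "rarely purchased both products in the same trial (11.94% of the trials"). Selection by BIC is complete: "the final model for all other outcome measures did not include this interaction". The power paragraph takes the smallest observed odds ratio, 2.8, from low-ventilation purchasing and concludes: "Using this effect size, the sample size of 20 participants, and an alpha of 0.05, we achieved 88% power in this study".

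**The concern.** An analysis plan has to name the factors that the trial manipulates. This protocol manipulates nicotine content, availability of alternatives and price. The SAP names session, ventilation level and the price of a product that the protocol does not have.

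If the protocol is the right document, the SAP cannot deliver what the study is for: demand by nicotine content, and substitution towards pouches and other products when they are on offer. A reader would then have no prespecified analysis against which to judge the published results. Any choice of outcome, contrast or model could have been made after the data were seen, and the SAP's own reporting of results would give no protection against that.

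**Working it through.** **1. The plan's own figure.** The only power figure is 88% (OR 2.8, 20 participants, alpha 0.05, 1000 simulations). The SAP does not give the baseline purchase probability, the between-participant SD, the number of trials per participant or the coefficient tested. The figure can therefore only be bracketed.

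With baseline p1, p2 = 2.8·p1/(1−p1) ÷ [1 + 2.8·p1/(1−p1)]. For m trials per level, n = 20m and p̄ = (p1+p2)/2, treating trials as independent,

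power = Φ{ [|p2−p1| − 1.96·√(2p̄(1−p̄)/n)] / √([p1(1−p1)+p2(1−p2)]/n) }.

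Example (assumed p1 = 0.3, m = 4): the odds are 0.4286 × 2.8 = 1.2, so p2 = 1.2/2.2 = 0.545, and n = 80. Power = Φ{(0.2455 − 0.1531)/0.0757} = Φ(1.22) = 0.889.

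The table gives ranges over assumed baselines of 0.1 to 0.5. The last column is from a random-intercept logistic simulation (20 participants, two-level within-person factor, stratified score test, 4000 runs, assumed SD 0.5 to 3).

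| Trials per level (m) | Formula | Simulation |
|---|---|---|
| 1 | 21–35% | 15–29% |
| 3 | 52–79% | 42–76% |
| 4 | 64–90% | 53–87% |
| 6 | 82–98% | 71–97% |
| 9 | not run | 86–100% |

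So 88% is attainable under some assumptions and is neither confirmed nor refuted. Either way it concerns a low-ventilation purchasing effect, so no corrected figure for the protocol's contrasts can be derived from it.

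**2. The documents side by side.**

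| | Protocol (2.1, 3.1, 5.1) | SAP |
|---|---|---|
| Cigarettes | 0.4 vs 17.4 mg/g nicotine | high vs low ventilation |
| Second factor | alternatives absent vs available | none; alternatives are an outcome only |
| Price varied | investigational cigarette, about 6 prices | HVC |
| Repeated structure | four conditions, one marketplace session (2.1) | 3 repeated measurements |
| Participants | up to 100 | 20 |
| Aims or outcomes | demand intensity, substitutability, complementarity | purchase yes/no, budget share, total cigarettes, perceived risk |

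The SAP text contains no mention of nicotine, mg/g or availability. The protocol contains no mention of ventilation, HVC or LVC.

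**3. Count of analyses.** Paired t-test, logistic model for HVCs, logistic model for LVCs and alternatives, ANOVA of budget share, ANOVA of total cigarettes: 5 analyses, 4 of them models. With nicotine content: 0. With availability: 0.

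**4. What would happen on the protocol's data.** The design has 2 × 2 × 6 = 24 cells per participant, taking about 6 prices as 6. Suppose the SAP's price term is carried over to the protocol's cigarette price, and session and ventilation have no counterpart. Price alone then has rank 6 of 24: it forms 6 groups of 4 cells. It is orthogonal to the nicotine, availability and interaction contrasts, so 0 of these 3 can be estimated. If all conditions were entered in the model for alternatives, nothing else is for sale in 2 × 6 = 12 of the 24 cells. The outcome would be 0 by design in half of them.

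**5. An impossible result.** The SAP reports trials in which both cigarette types were bought. In conditions 1 and 2 only one cigarette is offered, so this cannot happen there.

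**The case against.** The best counter-argument is that session is undefined in the SAP, and section 5.1 of the protocol itself introduces the four set-ups as sessions. If session meant condition, its four levels would span all 3 condition contrasts. Session plus price would have rank 4 + 6 − 1 = 9, and session by price rank 24. The result of 0 of 3 therefore depends on how one word is read, and the possible range is 0 to 3. The reading is unlikely, because the SAP ties its design to 3 repeated measurements and section 2.1 of the protocol has one marketplace session under four conditions. Even under it, ventilation level and HVC price would still have no data behind them.

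Other points deserve credit:

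- The SAP does relate purchases of alternatives to a cigarette price, which is a cross-price analysis in binary form. It is not silent on substitution as a concept, but it uses the price of a product absent from this protocol.
- Up to 100 is a recruitment ceiling, so an analysed number of 20 does not by itself contradict it.
- Ventilation cannot stand in for nicotine content. The SAP uses it for specification changes over time, with two values within each cigarette type.
- If the SAP is the right document, its models may suit its own study, and the fault is only that the wrong protocol accompanies it.
- Part of the SAP file was removed before review. It might identify the study, but it could not make these models fit this design.

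What stands is that the cell and rank counts are illustrative. The mismatch does not depend on them.

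**Conclusion.** The concern holds and must be fixed. The SAP and the protocol describe different studies: neither factor defining the protocol's conditions appears in any of the 5 SAP analyses, and the SAP's ventilation and HVC-price terms have no data in the protocol. As written, the SAP cannot be run on this trial. It is also a report of completed analyses, so it could not serve as a prospective plan even for its own study. The 88% power gives no assurance for the protocol's contrasts.

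Confidence is high for the mismatch itself. Which document is misplaced, and why, cannot be settled from the text available. The consequences for demand and substitution analyses assume that the protocol is the right document. The result of 0 of 3 contrasts further assumes that session is not the protocol's condition.

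**What to change.** First, establish which document belongs to this record and supply its matching counterpart. If it is the SAP, supply the protocol of the ventilation study. If it is the protocol, replace the SAP with one that:

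1. analyses purchases of the manipulated cigarette by nicotine content, availability of alternatives (conditions 1–2 against 3–4) and price, allowing for repeated measures within participant. A mixed model with the relevant interactions would do, as would per-participant demand-curve indices compared within subject; the choice is the sponsor's, but it should be stated;
2. analyses purchases of alternatives, nicotine pouches included, against cigarette price in conditions 3 and 4 only, by nicotine content;
3. carries no ventilation, HVC or LVC terms and no 88% power claim;
4. states whether it was written before or after data were seen, and is labelled post hoc if after.

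The cost is one replaced or rewritten document. No new data are needed, because both analyses use purchases that section 5.1 already plans to collect. If data have been seen, prespecification cannot be recovered and the label is the only remedy.

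### The purchase models name one random term per participant and none for session within participant, so the session test is too liberal if a person's purchasing shifts between sessions

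*SAP*

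**What the plan says.** All references are to the SAP, section Statistical Analysis Plan.

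- **Unit of analysis.** The outcome for the purchase models is binary: "whether or not a participant purchased that type of cigarette in a trial". The data therefore have one row per trial.
- **Random part.** The HVC model has session, ventilation level and HVC price as fixed effects, "with a random effect for each participant due to the repeated (3) measurements study design". No other random term is named.
- **Other products.** The structure carries over by one word: "Similarly, the purchasing of LVCs and alternative tobacco products was estimated using a mixed-effects logistic regression".
- **Model selection.** Only a fixed term was up for selection: "the inclusion of the interaction between session and price of an HVC was determined by the model with the lowest Bayesian Information Criteria". The purchase models ended without that interaction.
- **Price coding.** "For these analyses, the price of cigarettes was categorical" comes after the text on the repeated-measures ANOVAs. It is not clearly meant for the logistic models.

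The sample size of 20 comes from the closing power paragraph.

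**The concern.** A session-by-price interaction could be a candidate term only if several prices were offered in each session. The data thus have three levels: price trials, sessions, participants. The reason given for the random term is the three repeated measurements, but a single term per participant, most naturally an intercept, absorbs only stable differences between people. It does not absorb a person's shift from one session to the next.

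Session is a fixed effect that is tested. Its proper error is the session-to-session variation within people, and the number of prices per session does not reduce that variation. Without a term for it, the precision of the session contrast is judged from trial-level noise alone, which shrinks as prices are added. The interval is then too narrow and the test rejects too often. Nothing in the selection step would reveal this: the interaction considered is an average effect, and no random term was a candidate.

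A second, separate source is variation between people in price response, which bears on the price test rather than the session test.

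**Working it through.** **Inputs from the SAP:** 20 participants, 3 repeated measurements (read as sessions), binary trial outcome, level 0.05. **Not given, so assumed:** prices per session, participant SD, session-shift SD, purchase rate, test type.

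**Price count.** The SAP says that both cigarette types were bought in 11.94% of trials. With complete data there are 20 × 3 × P trials. For P = 6 that is 360, and 43/360 = 11.94%. No other P from 4 to 10 gives 11.94% with complete data: for example 36/300 = 12.00% at P = 5 and 57/480 = 11.88% at P = 8. With some missing trials other counts fit (48/402 at P = 7, 53/444 at P = 8). Six is therefore a reasonable working value, not an established one.

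**Scale of the assumed shifts.** A one-SD session shift moves a 50% buyer to 1/(1 + e^−0.5) = 62% at SD 0.5, and to 1/(1 + e^−1) = 73% at SD 1.0.

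**Rough hand check.** A person's session mean on the logit scale has trial-level variance of about 1/[P·p(1−p)]. A session shift with SD σ multiplies the variance of the session contrast by about 1 + σ²·P·p(1−p). A 2-df test at 0.05 then rejects with probability of about 0.05^(1/factor). With P = 6 and p = 0.5, P·p(1−p) = 1.5:

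- σ = 0.5: factor 1.375, rejection 0.05^(1/1.375) = 11%
- σ = 1.0: factor 2.5, rejection 0.05^(1/2.5) = 30%

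These are on the high side, because p(1−p) is below 0.25 for most people when participants differ widely.

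**Simulation of the session test** (2 df, no true session effect, single random intercept; 20 participants × 3 sessions × 6 prices). The first five rows use participant SD 1.5. The first four also use a purchase rate of about 50% and include a two-level ventilation term.

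| Run | SD 0 | SD 0.5 | SD 1.0 |
|---|---|---|---|
| Price linear, likelihood ratio, 1,000 runs | 4.4% | 9.4% | 17.8% |
| Price linear, Wald, 1,000 runs | 3.5% | 9.0% | 17.3% |
| Price categorical, likelihood ratio, 1,000 runs | 5.9% | 10.3% | 20.6% |
| Ventilation changing between sessions, 1,000 runs | 5.3% | 9.9% | 18.6% |
| Separately coded, no ventilation term, Wald, 2,000 runs | 5.2% | 9.0% | 18.8% |
| Further check, 500 runs | 3.0% | 7.2% | 18.6% |

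The Monte Carlo standard error near 5% is 0.7 points with 1,000 runs.

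**Sensitivity, at SD 0.5 and 1.0.** Participant SD 1.0: 8.9%, 21.5%. Participant SD 2.5: 8.7%, 17.4%. Purchase rate about 27%: 10.3%, 20.4%. Four prices: 7.3%, 12.9%. Ten prices: 11.3%, 28.6%.

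**With a session-within-participant intercept, at SD 0, 0.5 and 1.0.** Likelihood ratio, categorical price, 400 runs: 5.0%, 6.2%, 5.0%. Wald, 600 runs: 3.8%, 4.5%, 7.5%.

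**Price test** (no true average price effect, 6 prices, single random intercept, 1,000 runs), at between-person slope SD 0, 0.5 and 1.0 logits per half price range. Linear price: 4.9%, 7.9%, 18.4%. Categorical price (5 df): 6.2%, 6.3%, 11.6%. With linear price, small-sample participant-clustered errors give 3.8%, 4.0%, 3.8% (1,000 runs), and a random price slope with Wald tests gives 3.5%, 6.8%, 7.8% (600 runs).

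The two sources act separately: session shifts alone left the price test at about 4%, and slope variation alone did not inflate the session test.

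**The case against.** The strongest reply is that no defect has been shown in these data. Every variance component above is assumed, the SAP gives no sign that session shifts were large, and the same warning fits many random-intercept models of repeated binary data. This stands as a limit on size: the inflation may be nil. It does not remove the gap, because session is tested and the layout makes a session-level term the natural one to include or rule out.

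A second reply is that the SAP never says intercept, and a one-sentence summary may leave out terms that were fitted. That is fair, so the refit is asked for only if the term was absent.

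A third is that how rich a structure 20 participants can support is a judgement call. This carries weight for a random price slope. It carries less for one extra intercept that matches the design.

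The price part is weaker in other ways too. A zero average effect of HVC price on HVC purchase is a strained null hypothesis, and with categorical price there is no real inflation at slope SD 0.5. A reader might infer that the price results are as exposed as the session results; the documents do not support that.

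A reader might also infer that the 88% power is overstated. The SAP does not say which coefficient the OR of 2.8 belongs to or which model was simulated, so the figure can be neither confirmed nor refuted.

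**Conclusion.** The point holds in conditional form. As described, the purchase models have no term for session-to-session shifts within a person. If such shifts are material, the session test is too liberal: about 7–10% instead of 5% at a session SD of 0.5 logits, and 17–21% at SD 1.0. With no shifts it is close to nominal (3–6%). These figures assume 20 participants, 3 sessions, 6 prices and participant SD 1.5 logits, and they rise with more prices per session.

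It would go too far to infer that any reported session or price effect is false. The SAP gives no variance components, intervals or p-values from which to judge that. The price question is secondary and matters mainly if price entered linearly. The point concerns only the SAP's logistic models; the Protocol describes a different experiment (nicotine content and pouches rather than filter ventilation).

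**What to change.** 1. State the random-effects structure, the test type and the price coding for each logistic model.
2. Unless it was already fitted, refit each model with random intercepts for participant and for session within participant, in R notation `(1 | participant) + (1 | participant:session)`. Report both variance components.
3. Base session inference on this fit, using likelihood-ratio or small-sample tests, and show the single-random-effect result beside it. If the session variance is near zero, the two will agree and the matter is closed.
4. As a secondary check, report the price effect with a participant-level bootstrap or small-sample participant-clustered errors, or with a by-participant price slope if it converges. Clustered errors on an ordinary logistic model give population-averaged odds ratios, which differ in meaning from those of the mixed model.

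**Cost.** A changed formula and a refit of existing trial-level data; no new data. Intervals may widen somewhat and fits may be singular with 20 participants (convergence was not scored in the simulations). Some small-sample excess may remain, such as the 7.5% above. If the extra variance is zero the power loss is small: in one assumed setting (session odds ratio 2.8, 6 prices, 400 runs) power was 89.5% with the single term and 88.8% with both. That setting is illustrative and does not reproduce the SAP's power figure.

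### Does letting BIC decide on the session × HVC price interaction leave a fault in the models where it was dropped?

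*SAP*

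**What the plan says.** The SAP, under Statistical Analysis Plan, models purchase of HVCs, and of LVCs and alternative products, by mixed-effects logistic regression on session, ventilation level and HVC price. Each participant has a "random effect for each participant due to the repeated (3) measurements study design". Budget share spent on cigarettes and total cigarettes purchased are analysed by RMANOVA on session and HVC price. Directly after the two RMANOVAs it adds: "For these analyses, the price of cigarettes was categorical". The price coding in the logistic models is not stated.

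On the interaction, the rule is that "the inclusion of the interaction between session and price of an HVC was determined by the model with the lowest Bayesian Information Criteria (BIC"). The outcome of the rule is disclosed: "the final model to predict the total quantity of cigarettes purchased included the interaction between session and price". That is the only outcome for which the term survived; of the rest, the SAP reports that "the final model for all other outcome measures did not include this interaction". The significance criterion is: "All statistical tests were considered significant at the < 0.05 level". The post hoc power paragraph uses "the sample size of 20 participants, and an alpha of 0.05"; it concerns one odds ratio of 2.8 and does not mention the interaction.

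The Protocol (5.1, Hypothetical Experimental Tobacco Marketplace sessions) says that "the price of cigarettes (investigational cigarettes) is manipulated (approximately 6 prices"), but for a task with nicotine-content cigarettes. It does not ask whether price response differs between sessions.

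**The concern.** Session and HVC price enter every model, and their interaction was a candidate in every model. Where it was dropped, the final model imposes one price effect on all sessions (on the log-odds scale for the binary outcomes). A reader then cannot tell a price response that was similar across sessions from one that differed but fell short of the BIC bar. The Tukey post hoc comparisons do not help: without the interaction they compare sessions or prices, not price response between sessions.

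The worry grows because two standards appear to operate side by side. Reported effects are judged at 0.05, while the interaction had to pass a criterion whose strictness rises with its degrees of freedom and with the n entered in BIC. If price response did differ, the single price effect would be an average over unequal session effects.

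**Working it through.** The SAP gives no figure for this point. Its 88% power relates to an odds ratio of 2.8 and has no bearing on the interaction. The check therefore asks how strict the BIC rule is, and whether the documents suggest that it misled.

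**Inputs.** 20 participants (SAP, post hoc power). 3 sessions (assumption, read from the three repeated measurements). 6 prices (assumption, borrowed from the Protocol's different task; the SAP gives no number). The n in BIC is unstated, so both readings are shown: rows, 20 × 3 × 6 = 360, or participants, 20.

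**Formula.** BIC keeps the interaction when the likelihood-ratio statistic exceeds df × ln(n). Here df = (3 − 1) × (6 − 1) = 10 for categorical price and (3 − 1) × 1 = 2 for linear price. The equivalent p is the chi-square tail beyond that threshold. The chance of keeping a real interaction comes from the noncentral chi-square, with noncentrality set so that a 0.05 test would have 90% power.

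| Price coding | n | Threshold | Equivalent p | Kept, at 90% power for a 0.05 test |
|---|---|---|---|---|
| Categorical, 10 df | 360 | 10 × 5.886 = 58.9 | 6e-9 | 0.85% |
| Categorical, 10 df | 20 | 10 × 2.996 = 30.0 | 0.0009 | 48.6% |
| Linear, 2 df | 360 | 2 × 5.886 = 11.8 | 0.0028 | 60.7% |
| Linear, 2 df | 20 | 2 × 2.996 = 5.99 | 0.05 | 90% |

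With 4 to 12 prices, the last column runs for categorical price from 14.7% down to under 0.01% (n = rows) or from 70.3% to 9.4% (n = 20). For linear price it runs from 65.3% to 52.8% (n = rows), or stays at 90% (n = 20).

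**Which rows apply.** Categorical price is stated only for the RMANOVAs, so the first two rows describe budget share. The logistic models could fall in any row. In the last row BIC and the 0.05 test coincide, and the concern disappears.

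**Did the rule shut interactions out?** Total quantity and budget share are both RMANOVAs with session and categorical HVC price. They share the same interaction df and presumably the same n, so they faced the same bar. Total quantity cleared it. Even if the bar was 58.9, it could be passed in these data. The 0.85% applies only to an interaction just large enough for 90% power at 0.05.

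**What do the models set out to show?** The logistic models relate purchase to session, ventilation level and price. The budget-share analysis evaluates the roles of session and price. Main-effects models address both aims. Neither document names a between-session difference in price response as a hypothesis or endpoint.

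**Would an added analysis settle it?** One joint test per outcome over four outcomes carries 1 − 0.95^4 = 18.5% familywise error if independent. Session-specific slopes with linear price mean 2 independent contrasts per outcome, 8 in all: 1 − 0.95^8 = 34%. In simulated data with 20 participants, 3 sessions and 6 categorical prices, at least one all-or-none cell appeared in 0.6%, 28% and 80% of runs as purchase became rarer, so some interaction terms would not be estimable. Clustered standard errors in place of the random effect may turn the estimates into population-averaged ones, not comparable with the SAP's mixed models.

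**The case for a change.** The strongest case for acting is this. The interaction was selected for one of the modelled outcomes, so differing price response is a live possibility in this dataset. For budget share, BIC is stricter than 0.05 at every number of prices examined and under either n. An interval for the dropped term would separate similar response from imprecise data, which silence cannot do. The work is a few sentences and some supportive refits on data already collected.

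Part of this stands. The SAP describes no estimate of the dropped term, the BIC arithmetic is right, and absence from a final model does not demonstrate equality. But this is a limit on what the analysis can show, not an error in what it does show. The SAP makes no claim that an estimate would correct. A main effect averages over any omitted interaction in every main-effects model, so that fact alone is no fault. The count of four outcomes is also inferred: LVCs and alternative products share one sentence, so it could be three, or more if each alternative product was modelled separately. Finally, statisticians would differ on the form of the added report (random slopes, clustered errors or a single joint test), and at 20 participants its results would often be wide or not estimable.

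**Conclusion.** No change to the plan follows. The rule is recognised and applied to all analyses, and its result is disclosed. Main-effects models answer the questions that the SAP poses, and the rule kept the interaction in one of the two categorical-price RMANOVAs.

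The size of the concern cannot be fixed from the documents. The chance of keeping an interaction that a 0.05 test would find with 90% power ranges from under 0.01% to 90%. It depends on the number of prices, the price coding in the logistic models and the n in BIC, none of which the SAP states. Three sessions and 6 prices are assumptions; only the 20 participants come directly from the SAP.

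Two things remain for the reader. A dropped interaction should not be taken as equal price response across sessions. The unstated coding, price count and n are ordinary reporting details that the analyst can supply on request. None of this shows a stated result or conclusion to be wrong.
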